5.4 Statistical Analysis Plan

The data from this study will be analyzed to determine whether the primary endpoints and study acceptance criteria (as recommended by FDA and as listed in section 5.2) were met.

In order to assure that 95% confidence in 95% reliability of the of the lower confidence level of the units meet the acceptance criteria for the primary endpoints, the sample size shall be:

- Ninety-three (93) evaluable procedures in which no more than one (1) failure occurs against the acceptance criteria for the primary endpoints.

Secondary analyses, such as differences in populations by site and comparisons between arms, will be described in more detail within the statistical analysis plan. This formal SAP will be developed in conjunction but separately from this protocol, and filed within the trial master file.

The following, at a minimum, will be presented using descriptive statistics:

- **Donor Disposition:** All data on all study donors enrolled in trial including data identified as evaluable and non-evaluable donations will be presented.
- **Demographics:** Age, gender, weight, height, ethnicity and race will be provided for all study donors enrolled in the trial for both evaluable and non-evaluable donations. A comparison to census data will be performed in the final report.
- **Collection procedure-related data:** Collection duration and ambient temperatures will be provided for both evaluable and non-evaluable donations.

Study Protocol

Clinical Investigation to Evaluate the New Health Sciences Hemanext® Oxygen Reduction System for Leukoreduced Red Blood Cells with CP2D Anticoagulant and AS-3 Additive - Pivotal Trial

Protocol #: CLIN-0001

Date: 28 Nov 2017

Page 20 of 65

- **Filtration & processing procedure-related data:** Temperature, head height, filtration time, filter time, filter weight, and final collection volumes will be provided for evaluable and non-evaluable donations.
- **Laboratory data:** Laboratory data will be provided for evaluable and non-evaluable donations (if applicable). Other than the endpoints detailed in the acceptance criteria, the laboratory data will be presented for information only.
- **Adverse events:** Expected, unexpected and serious adverse events will be reported for all enrolled study donors.

6.0 Test Material and Study Methodology

6.1 Test Material

Disposables directly related to the IP will be labeled as an investigational product.

6.1.1 Product Storage, Accountability and Disposition

Study product will be supplied by NHSi after the study contract has been executed. Study product may not be used in any capacity until proof of IRB approval and IRB-approved informed consent(s) for the study have been received by the Sponsor. Site documentation of 100% accountability of the IP is required beginning with receipt of the product until all product has been dispensed, destroyed and/or returned to the study sponsor. A "Study Product Receipt and Disposition Log" will be supplied by NHSi in the Clinical Trial Binder for documenting each receipt and disposition (i.e., used, discarded or returned) of the study product. The IP are to be stored at room temperature in a secure location upon receipt. Unused product will be returned to the sponsor at the end of the trial unless other documented instructions are provided in advance to the respective clinical site.

6.2 Methodology

6.2.1 Tare Weight Measurements

During the study initiation visit and prior to enrolling the first study donor, tare weight measurements must be determined for the IP. Tare weight instructions and source documents will be supplied within the study's Regulatory Binder, and tare weights will be obtained and confirmed at the individual study sites. Tare weight data must be entered onto the sponsor-provided worksheet(s) and into the appropriate eCRF within the study's EDC system.

All blood and blood component weight measurements will be gross weight measurements. Each site participating in the clinical trial will either be provided with a prepared Tare Kit or will develop a Tare Kit during the SIV. The Tare Kits are to be retained until the completion of the study.

Study Protocol

Clinical Investigation to Evaluate the New Health Sciences Hemanext® Oxygen Reduction System for Leukoreduced Red Blood Cells with CP2D Anticoagulant and AS-3 Additive - Pivotal Trial

Protocol #: CLIN-0001

Date: 28 Nov 2017

Page 21 of 65

NOTE: The ORB component of the Hemanext RBC Processing system must be weighed individually and cannot be a part of a standard Tare Kit.

6.2.2 Donor Selection, Consent and Enrollment Rate

This study will enroll up to 93 evaluable study donors (see sections 5.3.2, 5.3.3 and 5.3.5 for details regarding intended enrollment, inclusion/exclusion criteria and donor evaluability determinations). Study donors will be selected from site-managed databases of known donors as well as new donors who meet study eligibility criteria. Clinical sites may choose to employ IRB-approved advertisements as a means to assist recruitment.

Individuals who express interest in study participation must undergo site-specific informed consent processes per local requirements. Study donors will be consented by the respective sites' PI or appropriate PI delegate(s) prior to undergoing any study-related activities or assessments using the respective sites' IRB-approved Informed Consent Form, and will follow consenting procedures per local SOP and 21CFR 50.27.

For the purpose of this study, any study donor who has signed the study's informed consent documentation is considered to be enrolled in the study regardless of whether the enrolled individual engages in any study activity beyond ICF signing, donates blood, or is evaluable.

Each study sites' rate of enrollment will be dependent on limitations resulting from both individual study donor's evaluability and sites' ability to process the required number of evaluable study donors per study arm. As a result, the distribution of evaluable study donors may vary per study arm and per site.

6.2.3 Study Donors: Assigning to Study Arm and Randomization to Study Product

Study donors must be randomized to either IP or CP prior to their first donation. A donor randomized to IP will donate their first whole blood unit to be stored with the Investigational Product, and will donate their second whole blood unit to be stored with the Control Product. A study donor randomized to CP will donate their first whole blood unit with the Control Product, and will donate their second whole blood unit with the Investigational Product.

The randomization process will be a manual process that will be recorded within the Subject Enrollment and Screening Log. The randomization procedure will be based on a form generated wholly with SAS that will provide sequentially listed randomized product. Further details regarding the randomization process and associated documentation will be captured within the study's Operation Manual. Documentation relative to randomization will be stored within the study's Regulatory Binder.

Study Protocol

Clinical Investigation to Evaluate the New Health Sciences Hemanext® Oxygen Reduction System for Leukoreduced Red Blood Cells with CP2D Anticoagulant and AS-3 Additive - Pivotal Trial

Protocol #: CLIN-0001

Date: 28 Nov 2017

Page 22 of 65

6.2.4 Whole Blood Collections

After study donors are consented, initial screen procedures have been completed, and individual donors have been assigned to their study arm and randomized, study donors will donate $500\text{mL} \pm 10\%$ of whole blood with each whole blood donation. Approximately 20 - 40mL of blood (included within the $500\text{mL} \pm 10\%$) will be collected during phlebotomy for CBC, ABO typing, TTD and SCT testing. The total volume of blood removed from any donor at collection will not exceed 550mL.

Study donors who also participate in the in vivo cohort will have whole blood samples of various volumes drawn as part of the cohort. The in vivo study does not require an additional whole blood unit donation. However, as part of the in vivo study, whole blood samples will be drawn on Day 42 (50-65 mL total) and additional whole blood samples will be drawn on Day 43 (10 mL) and 5ml for each subsequent time point for in vivo survival. See section 6.2.11 for details.

6.2.5 Leukoreduction of Whole Blood Units

Each collected whole blood unit will be leukoreduced warm using the leukoreduction filter per the IFU for the Haemonetics WB Leukotrap System (Appendix 13.2). The collection set with leukoreduction filter will be used according to the instructions for use provided at study initiation with the head height specifications included.

6.2.6 Slow Filtrations

Any filtration with a Bag Empty Time (emptying of the Donor Bag) that is greater than one hour will be considered a slow filtration. Slow filtrations will be documented, the Sponsor will be notified immediately and testing will continue to completion if the product is stored in < 12 hours for the IP or < 8 hours for the CP groups.

6.2.7 Whole Blood Processing and Preparation of PRBC

As dictated, each leukoreduced whole blood unit will be processed into PRBCs and platelet-poor plasma (PPP) using a representative hard-spin centrifugation and subsequent aspiration (PRBC/PPP separation).

The PRBC unit will be mixed with the AS-3 additive per the product's instructions for use. PPP will not be analyzed, and this plasma will be discarded per Section 6.2.12.

6.2.8 Blood Product Sampling

Blood product containers will be thoroughly mixed prior to sampling to ensure a representative sample is obtained from a homogeneous blood product.

Study Protocol

Clinical Investigation to Evaluate the New Health Sciences Hemanext® Oxygen Reduction System for Leukoreduced Red Blood Cells with CP2D Anticoagulant and AS-3 Additive - Pivotal Trial

Protocol #: CLIN-0001

Date: 28 Nov 2017

Page 23 of 65

Thorough mixing of each whole blood unit prior to taking pre-filtration and post-filtration samples is of critical importance for the calculation of filtration red cell recovery.

All sample aliquots will be taken without damaging the integrity of the test system or blood unit. Evaluation samples from whole blood and RBC units will be taken via a sterile connection between a sterile transfer bag to the blood product container using an FDA approved sterile connection device and then transferring an aliquot to the transfer bag.

When sampling, care must be taken to ensure that air is not transferred to the blood component container from the sample transfer bag. If a red cell unit is removed from cold storage for sampling purposes it must be returned to cold storage (1-6°C) within 30 minutes of the time of removal.

6.2.9 Microvascular Analysis

This study incorporates an evaluation of deformability using an experimental assay to characterize red cell deformability called the Microvascular Analyzer (MVA). The MVA measured perfusion of an artificial microvascular network under physiological conditions. Additional details on the procedure for this assay are documented in the study operations manual. This testing will only be performed on donors participating in the in vivo portion of the study.

For the purposes of this study, the assay will be considered optional and inability to complete it will not be documented as a protocol deviation. The Sponsor and sites may mutually agree to discontinue the testing at any time should difficulties with the equipment be encountered.

6.2.10 Laboratory Storage and Testing Methods

All study blood products will be stored under standard blood banking conditions. All study blood products will be segregated from normal blood product inventory. PRBC units are stored for 42 days at 1-6°C.

All testing will be conducted using laboratory equipment and instruments that are in current calibration, according to site standard procedures or using a validated scientific method. Site research laboratory standard procedures for testing performed in the study are to be available for inspection by the Sponsor. When study testing is performed by a certified clinical laboratory, copies of current CLIA and/or CAP certification must be provided to the Sponsor.

Refrigerators used to store blood products will be equipped with a temperature recorder or linked to a temperature recording system that will alarm and initiate contact with site staff when out of the protocol-indicated temperature ranges.

Study Protocol

Clinical Investigation to Evaluate the New Health Sciences Hemanext® Oxygen Reduction System for Leukoreduced Red Blood Cells with CP2D Anticoagulant and AS-3 Additive - Pivotal Trial

Protocol #: CLIN-0001

Date: 28 Nov 2017

Page 24 of 65

6.2.11 Radiolabeled Red Cell Procedures

This study incorporates an in vivo cohort to evaluate Day 42 RBC recovery and subsequent survival. Measures to ensure the study donor receives his or her own (autologous) radiolabeled red cells begin at donation when the study donor's name, birth date and unique identifying number will be recorded on the donor registration form. Clinical sites must have a standard labeling and handling process intended to eliminate errors in linking packed RBC units with the correct study donor.

On the first day of each in vivo cohort (42-days following each donation for in vivo cohort participants), female study donors must not be pregnant as determined by a negative pregnancy test (whether urine and/or serum pregnancy tests are used will be dictated by local procedures; women who are post-menopausal or surgically sterile may be exempt from the pregnancy test requirement if allowed by local procedures). The outcome of the pregnancy test will be recorded in both the source documentation and EDC.

RBC survival testing will be performed at 24h (± 1 h), 48h (± 4 h), 72h (± 4 h), 7 days (± 1 day), 14 days (± 1 day), 21 days (± 1 day), and 28 days (± 1 day).

Radiolabeling RBC procedures are derived from the literature (Davey, 1987; Heaton, 1992). However, individual clinical sites will follow specific local labeling, infusion, sampling and recovery/mass determination procedures and SOPs.

6.2.12 Blood Product Disposition

Each whole blood unit collected in the study will generate one unit of RBC in additive solution and one unit of PPP. All additive RBC units are to be discarded per site procedure after completion of the study following receipt of Sponsor's written consent. 51Cr and 99mTc-labeled RBC samples will be discarded following receipt of written permission from the sponsor and will be discarded per study site-specific SOP relative to the destruction of radiolabeled biological materials. Written consent will not be required for any unit with a confirmed positive infectious disease result.

6.2.13 Endpoint Calculations

Study sites will perform real-time calculations (RBC mass) and batch testing (hemolysis) to determine whether study endpoints meet study criteria and specifications. Clinical sites will employ the formulas that follow to perform real-time calculations for the purpose of informing the study sponsor quickly when it appears that data relative to the study acceptance criteria appear to be out of the acceptable range. However, for the purpose of the database and resulting data, the raw values will be entered into the EDC database, and the reported values will be calculated separately.

Study Protocol

Clinical Investigation to Evaluate the New Health Sciences Hemanext® Oxygen Reduction System for Leukoreduced Red Blood Cells with CP2D Anticoagulant and AS-3 Additive - Pivotal Trial

Protocol #: CLIN-0001

Date: 28 Nov 2017

Page 25 of 65

24-hour in vivo RBC recovery and survival will occur per the procedures summarized in section 6.2.11, and clinical sites will use the raw data to perform their own 24-hour % RBC recovery and survival calculations. Only % Recovery and % Survival values will be entered into the study's EDC system. Formulas used and the means to perform calculations relative to RBC recovery are site-specific. Calculated values will be confirmed per data captured within the eCRF relative to confirmation of calculations during monitoring visits.

Upon performing calculations for recovery, should a calculated value fall outside of the protocol-specified endpoint criteria, then the sponsor will be notified as soon as possible and within 24 hours.

Study Protocol

Clinical Investigation to Evaluate the New Health Sciences Hemanext® Oxygen Reduction System for Leukoreduced Red Blood Cells with CP2D Anticoagulant and AS-3 Additive - Pivotal Trial

Protocol #: CLIN-0001

Date: 28 Nov 2017

Page 26 of 65

6.2.14 RBC Filtration Recovery Calculation

RBC filtration recovery will be calculated via both a standard and the alternative method (using post filtration and pre-filtration weights). These calculations will be performed during the data analysis phase of the study based on hematocrit, volume and pre-/post filtration weights provided by sites. To better ensure accurate data, it is recommended that unit volumes be calculated from the weight of the full product. The results from both calculations will be reported.

RBC filtration recovery will be determined according to Figure 4. The acceptance criteria will be determined by the "standard equation" below.

Figure 4: RBC Recovery calculations (Standard and Alternate equations)**Standard equation:**

$$\text{RBC Recovery} = (\text{A} \times \text{Post-filtration unit volume}) / (\text{B} \times \text{Pre-filtration unit volume}) \times 100$$

Where: 'A' = Post-Hemanext HCT or RBC count

'B' = Pre-filtration HCT or RBC count

Unit volume (mL) = unit weight (g) / 1.056 (g/mL)

1.056 = relative density of whole blood

Alternate equation:

$$\text{RBC Recovery} = (\text{Post-filtration net unit weight}) / (\text{Pre-filtration net unit weight}) \times 100$$

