5.2 Study Primary Endpoints and Acceptance Criteria

The primary endpoints that will be evaluated in this clinical trial are RBC mass recovery, hemolysis and 24-hour in vivo red cell recovery. The endpoint-associated study acceptance criteria are listed below:

- A one-sided 95% lower confidence limit for the true proportion of packed RBC units with hemolysis at day 42 of < 1% is > 95%.
- The mean 24-hour, post-transfusion, in vivo red cell recovery of at least 75% with a standard deviation of $\leq 9\%$, and the lower limit of a one-sided 95% confidence interval for the population proportion of successes is $\geq 70\%$.
- Red Blood cell recovery $\geq 85\%$; with 95% confidence that at least 95% of units are $\geq 85\%$.

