5.3 Donor/Data Criteria**5.3.1 Sample Size**

The sample sizes described within the protocol were selected to demonstrate meeting study primary endpoints that conform to the FDA's 95-95 rule (95% confidence and 95% reliability). For successful endpoint outcomes, the study requires meeting the acceptance criteria in 92 of 93 test units per test condition. Therefore, 93 evaluable study donors will complete the study. In the event of two (2) donors/units with unmet acceptance criterion occurring out of ninety-three (93) evaluable procedures (i.e., within one or more study arm(s) for one or more acceptance criteria/primary endpoints), the study will be discontinued.

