6.2.16 Study Activities

Study donors who are eligible for study participation will be assigned to either the in vitro portion only or in vivo and in vitro groups. Study donors will be enrolled until the intended total of evaluable units has been collected. Note that cited days reference the number of days post collection.

See Tables 5-7 for summary of analyses and data collection.

Study Protocol

Clinical Investigation to Evaluate the New Health Sciences Hemanext® Oxygen Reduction System for Leukoreduced Red Blood Cells with CP2D Anticoagulant and AS-3 Additive - Pivotal Trial

Protocol #: CLIN-0001

Date: 28 Nov 2017

Page 27 of 65

- a) After signing the respective consent documentation, collect and record data relative to inclusion/exclusion criteria, demographics, concomitant medications and medical history.
- b) Collect and record the collection set's identification numbers.
- c) Collect a whole blood unit using the product per the IFU. Draw a sample of the study donor's native whole blood from the diversion bag and place aliquots in tubes for the indicated analyses.
- d) As soon as reasonably possible after collection, place anticoagulated whole blood units into room temperature storage until filtration.
- e) Immediately prior to filtration, weigh, sample and re-weigh each whole blood unit.
- f) Initiate room temperature filtration for each unit (5-7 hours post-collection). Record filtration-associated data.
- g) Weigh, sample and then re-weigh filtered whole blood units.
- h) As soon as practical following the completion of filtration, the LRWB units will be centrifuged and processed at room temperature to separate the unit into PRBCs and PPP. Record centrifugation-associated data.
- i) AS-3 will be mixed with the PRBCs as soon as practical following separation from the plasma.
- j) Following processing, the additive RBC unit will be weighed.
- k) Plasma will be discarded.
- l) The unit will be sampled and weighed.
- m) If the unit is in the CP arm then at this point it will be placed in refrigerated storage (1-6°C; within 8 hours of donation).
- n) If the unit is in the IP arm then the AS-3 LR-RBC unit will be transferred to the Hemanext ORB (within 8 hours of donation) at which point the unit will be weighed to ensure that the volume of the unit is less than 350 mL.
- o) The ORB will be placed on a Helmer Platelet Shaker for 3 hours + 15 minutes.

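### If RBC recovery runs from pre-filtration to post-Hemanext, Figure 4 counts the protocol's own blood samples as device loss against the 85% primary criterion

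*Combined protocol and SAP*

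**What the plan says.** Section 5.2 makes RBC recovery a primary endpoint: each unit is judged at 85%, "with 95% confidence that at least 95% of units are" at or above that level. Section 5.3.1 turns this into a count: "For successful endpoint outcomes, the study requires meeting the acceptance criteria in 92 of 93 test units per test condition". If two units fail, "the study will be discontinued".

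Section 6.2.14 gives a standard and an alternate equation and lets the standard one decide the criterion. It is A times post-filtration unit volume, divided by B times pre-filtration unit volume. A is the post-Hemanext hematocrit or RBC count, and B is the pre-filtration value. Volume is unit weight divided by 1.056. On inputs it says: "These calculations will be performed during the data analysis phase of the study based on hematocrit, volume and pre-/post filtration weights provided by sites". It recommends using the weight of the full product, without naming the pre-sample or post-sample weight.

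Section 6.2.16 removes blood repeatedly along the way. Step e: "Immediately prior to filtration, weigh, sample and re-weigh each whole blood unit". Step g: "Weigh, sample and then re-weigh filtered whole blood units". Step l, on the additive unit at Baseline: "The unit will be sampled and weighed". Step p samples again after Hemanext processing. Section 6.2.13 carries the equation to the sites: "Clinical sites will employ the formulas that follow to perform real-time calculations".

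**The concern.** A recovery ratio is meant to show what the filter and device lose. If its two ends are pre-filtration and post-Hemanext, as B and A indicate, the samples at steps g and l lie inside the interval. Those cells were taken by the protocol, but the equation treats them as not recovered. The step-e sample joins them if the denominator uses the weight taken before that sample.

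The error runs one way: uncounted samples can only lower reported recovery. The criterion is applied unit by unit with one failure allowed, so a modest downward shift can matter. A unit that lost less than 15% of its cells to processing could be recorded as a failure, and two such units would discontinue the study.

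**Working it through.** **1. The plan's own figure.** With a true failure rate of 5%, the chance of at most one failure in n units is 0.95^n + n × 0.05 × 0.95^(n−1). At n = 92 this is 0.0521; at n = 93 it is 0.04998. So 93 with at most one failure is reproduced. The exact one-sided 95% lower limit is 95.0006% for 92/93 and 93.4% for 91/93. The rule has no slack for one extra false failure.

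**2. Where the samples fall for a test unit (section 6.2.16).**

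| Step | Stage | Position relative to B → A |
|---|---|---|
| e | pre-filtration | at the start; counted as loss if the pre-sample weight is used |
| g | post-filtration | inside |
| l | Baseline, additive RBC | inside |
| p | post-Hemanext | at the end; counted as loss if the post-sample weight is used |

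**3. Formula.** Let R be the true process recovery (the product of the step recoveries), s_g and s_l the volumes sampled at steps g and l, and V_g and V_l the unit volumes at those stages. With the post-sample weight at the start and the pre-sample weight at the end,

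reported recovery = R × (1 − s_g/V_g) × (1 − s_l/V_l).

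Using the pre-sample weight at the start adds a factor (1 − s_e/V_e).

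**4. Break-even, with no volumes needed.** Reported recovery reaches 85% when the sampled fraction is 1 − 85/R. For R = 90% this is 5.6%; for R = 92% it is 7.6%.

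**5. Assumed volumes.** The documents bound the collection (500 ± 50 mL) and the LR RBC unit (at most 350 mL) but give no sample volumes. Assume V_g of 480 to 550 mL and V_l of 300 to 350 mL.

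| s_g + s_l | Fraction retained | True R needed to read 85% | R = 90% reads | R = 92% reads |
|---|---|---|---|---|
| 5 + 10 mL | 0.957–0.963 | 88.3–88.9% | 86.1–86.6% | 88.0–88.6% |
| 10 + 20 mL | 0.914–0.926 | 91.8–93.0% | 82.2–83.3% | 84.1–85.2% |

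The loss is therefore about 4% in the first row and 7.4 to 8.6% in the second.

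**6. Choice of weight at step e.** Assume samples of 10, 10 and 15 mL from units of 570, 530 and 335 mL. With the post-sample weight at the start, the retained fraction is (1 − 10/530)(1 − 15/335) = 0.937, and a true 92% unit reads 86.2% and passes. With the pre-sample weight it is 0.937 × (1 − 10/570) = 0.921, and the same unit reads 84.7% and fails. The unstated choice can decide the unit's result.

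**7. Effect on the 93-unit rule.** Assume normal true recovery with SD 2%, V_g = 500 mL and V_l = 330 mL. The failure probability per unit is Φ((85/f − mean)/2), where f is the retained fraction; the last three columns give the probability of at most one failure in 93.

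| Mean true R | Sampling accounted for | 5 + 10 mL, not accounted for | 10 + 20 mL, not accounted for |
|---|---|---|---|
| 92% | 1.00 | 0.095 | about 0 |
| 95% | 1.00 | 0.998 | 0.001 |

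**The case against.** The strongest objection is that the documents do not settle the interval. The section title refers to filtration recovery, the numerator volume is labelled post-filtration, and section 6.2.8 ties thorough mixing before the pre- and post-filtration samples to this calculation. On a pre- to post-filtration interval the Baseline sample is outside. The step-g sample is outside too if the pre-sample weight is used at the end. Only the step-e weight choice then remains. This stands, and it is why the point is conditional. Against it, A is explicitly post-Hemanext.

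The equation taken exactly as printed does not produce the false failures shown above. It multiplies a post-Hemanext hematocrit by a whole-blood volume. With assumed hematocrits of 52–60% and 34–40% and volumes of 500 and 520 mL, it returns about 125% to 170%, which cannot be interpreted as recovery. The sampling error appears once the stages are aligned at post-Hemanext.

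There are mitigations. Section 6.2.13 says raw values go to the database and reported values are calculated separately, so an apparent failure could be recalculated. The bias cannot make a poor device pass. The separate SAP might name the weights, but section 5.4 refers to it for secondary analyses, while section 6.2.14 fixes the deciding equation.

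A reader might infer that the Baseline draw is large because many assays are listed, or that the bias differs between sites because draws differ. No draw volume is given for any stage or site, so neither inference is supported.

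**Conclusion.** Wrong as written, and should be fixed. If recovery is measured from pre-filtration to post-Hemanext, the deciding equation counts the step-g and step-l samples as device loss and leaves the step-e weight open. That structural point follows from the text and needs no assumed volumes.

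The size does not follow from the text. It rests on assumed sample volumes, unit volumes and true recovery. Small samples with high true recovery would cause few or no false failures; samples of 10 + 20 mL would bring a true 90% unit below 85% and a true 92% unit to about the limit. A reader might infer that the trial will fail this endpoint through sampling, or that a 92% unit fails even with small draws. The documents support neither: with 5 + 10 mL, or with 10 + 15 mL from 530 and 335 mL and the post-sample starting weight, a 92% unit passes.

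**What to change.** Make one edit to Figure 4, together with the edit that reconciles the numerator's volume stage with A:

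- Denominator: post-sample net weight at pre-filtration.
- Numerator: pre-sample net weight at the chosen end stage.
- For each sampling inside the interval, add to the numerator the red-cell mass removed: (pre-sample minus post-sample weight)/density × hematocrit or RBC count at that stage. Alternatively, multiply stepwise recoveries, each being the pre-sample end mass over the previous step's post-sample start mass. The two differ only slightly, because the add-back credits sampled cells with no later loss; specify one in advance.
- Use the same formula in the SAP and in the sites' real-time check, since apparent failures bear on the two-failure stop.

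The cost is wording in the protocol, SAP and site worksheet. Sections 6.2.16.4, 6.2.16.6, 6.2.16.8 and 6.2.16.10 already record pre- and post-sample weights, hematocrit and RBC count at each stage. No new tests, samples or donors are needed.
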